In addition, [name] is serving as a co-mentor and co-investigator on the proposed project. [name] is Professor and Director of Clinical Training at Ryerson University. [name] previously served as Deputy Director of the Women's Health Sciences Division at the National Center for PTSD in Boston as has an extensive research track record including serving as PI on several VA and NIH funded treatment development research studies focusing on designing couples therapies. [name] combination of expertise in couples therapy treatment development, women's health, and Veterans health is an ideal compliment to [name] mentorship team.

4. RESEARCH DESIGN AND METHODS (including data analysis)

A. Overview

The primary objective of this study is to examine the extent to which oxytocin improves couples' conflict resolution skills and mitigates their subjective, physiological, and neuroendocrine responses to this common stressor. Couples in which one or both partners have a recent history of substance abuse will be recruited. The present study will take place over one visit. In addition to a thorough psychosocial evaluation conducted by a trained clinician, couples will complete two laboratory conflict resolution tasks. Prior to the start of the second conflict resolution task, both partners will be administered a 40 IU dose of intranasal oxytocin. The flow chart below illustrates each element of the study:

B. Subjects

Thirty-six couples (N=72 individuals total) will be recruited to participate in the proposed study. Respondents will be screened by phone and provided all pertinent information about the study. Inclusion criteria are: 1) 18-65 years of age, 2) both partners are willing to participate, and 3) at least one partner has engaged in hazardous drinking (i.e. 4 or more drinks for women, 6 or more for men) or illicit drug use during the past 60 days. Exclusion criteria are: 1) pregnancy for women, 2) current psychotic or bipolar disorders, 3) active suicidal or homicidal ideation and intent, 4) subjects who would

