Potential Risks. Research participation may result in psychological distress as a result of the conflict resolution task, from disclosing personal or sensitive information about their health, their history, or their relationship within the self-report or interview portions of data collection. Loss of confidentiality is a risk of participation. Risks associated with intranasal oxytocin have been noted among women given intravenous, rather than intranasal, oxytocin for its FDA-approved purpose, to induce labor. These risks include seizures, mental disturbances, nausea, vomiting, irregular heartbeat, high blood pressure, and unexpected bleeding or contraction of the uterus and have been observed in a small number of women. However, preliminary studies conducted by the PI, [name], and senior researchers in our department and others conducting clinical trials in this area indicate that risks of intranasal oxytocin administration at the planned dose of 40 IU is minimal and manageable through the proposed human subjects protection methods described below. All possible efforts to minimize participant burden and distress will be made. All possible efforts will also be made to protect the confidentiality of participants' data, except in the event of imminent risk to self or others, or in the event of disclosure of child or elder abuse. In the event that confidentiality must be broken to protect the safety of participants or others, only the data essential to make an adequate report to authorities will be disclosed. All participants will review the IRB-approved informed consent document with research staff in a private room separate from their partner. Through this process, research staff will inform all research participants of the risks of participation, including emotional distress. In the event that a participant experiences substantial distress or reports risk of harm to oneself or others, they will be asked to complete a safety plan and if necessary, call 911. The Mobile Crisis Unit of Charleston County and urgent care services on the MUSC campus are additional resources available to study staff and research participants. [name] are licensed clinical psychologists equipped to help participants effectively manage their distress and to evaluate conditions in which participants may need additional assistance. In the event that a participant becomes distressed during or following an assessment, the PI will also contact the participant the following day to ensure they have received resources necessary, and to assess their

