Regulatory Issues. All Adverse Events (AEs) that meet criteria for reportable AEs will be reported to the MUSC IRB and NIH within 10 working days. AEs are reportable if the AE is unexpected AND related or possibly related AND serious or more prevalent than expected. The IRB definition of unexpected is that the AE is not identified in nature, severity or frequency in the current protocol, informed consent, investigator brochure or with other current risk information. The definition of related is that there is a reasonable possibility that the adverse event may have been caused by the drug, device or intervention. Serious AEs (SAEs) will be reported within 24-hours. Follow-up of all unexpected and serious AEs will also be reported to these agencies. All AEs are reviewed weekly by the PI, and annually by the Data Safety Monitoring Board (DSMB) and IRB. Any significant actions taken by the local IRB and protocol changes will be reported to NIDA. AEs and SAEs occurring during the course of study will be collected, documented, and reported in accordance with protocol and IRB reporting requirements. All research staff involved with adverse event reporting will receive training including identification, evaluation, and documentation and reporting. All research staff will identify any potential AEs during the course of the study from self-report data and administration of assessments and interviews. This information will be provided to the PI and Co-Investigators, who will be responsible for AE/SAE assessment and evaluation including a determination of seriousness and study relatedness.

Definition of AE and SAE

Anticipated Risk - Mild to moderate discomfort when completing the laboratory assessment is anticipated and is not considered an adverse event for this study. Potential for relapse of alcohol and or drug use is anticipated and relapse is not considered an adverse event for this study. Potential for inpatient detoxification following a relapse is not unexpected among some subjects, particularly subjects with a prior history of medically supervised detoxification, and is not considered an adverse event for this study.

Adverse Event- An untoward medical event among randomized subjects occurring during a clinical study that can represent a new symptom experienced by a study subject or an exacerbation or worsening of an existing condition.

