Serious Adverse Event- Any untoward medical event or adverse drug experience occurring at any dose that results in any of the following outcomes:

- 1) Death.
- 2) A life threatening event.
- 3) Requires or prolongs inpatient hospitalization
- 4) Persistent or significant disability/incapacity.
- 5) A congenital anomaly or birth defect.

Important medical events that may not result in death, be life-threatening or require hospitalization may be considered a serious adverse experience when, based upon appropriate medical judgment, they may jeopardize the subject and may require medical or surgical intervention to prevent one of the outcomes listed in this definition.

Documentation and Reporting:

Any clinical study event that is judged to be an AE will be recorded on the AE Form during the course of the study. The PI ensures this information is captured during every study subject visit. If the AE is not serious, the information is recorded, managed medically as appropriate, and the event is followed until resolution. AEs are reportable if the AE is unexpected AND related or possibly related

AND serious or more prevalent than expected. All three criteria must be met for an AE to be a reportable AE. The IRB definition of unexpected is that the AE is not identified in nature, severity or frequency in the current protocol, informed consent, investigator brochure or with other current risk information. The definition of related is that there is a reasonable possibility that the adverse event may have been caused by the drug, device or intervention. SAEs are also recorded on the AE Form, managed medically as appropriate, and the event is followed until resolution. In addition, the PI reviews all completed AE forms for determination of SAE that require reports to the Sponsor. The PI informs the Sponsor immediately of knowledge of a SAE. As additional information becomes available on the SAE, it will be forwarded to the Sponsor. All SAE reports shall be sent to the IRB and NIH within 24 hours of learning of event occurrence.

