AEs/SAEs are documented and reported as per protocol and IRB requirements. Research staff will identify adverse events and obtain all available information to assess severity, seriousness, study relatedness, expectedness, outcome and the need for change or discontinuation in the study intervention. Additional relevant AE information if available will be documented in a progress note in the research record as appropriate to allow monitoring and evaluating of the AE. If the AE meets the definition for serious, appropriate SAE protocol specific reporting forms are completed and disseminated to the appropriate persons and within the designated timeframes as indicated above. For each AE/SAE recorded, the research staff will follow the AE/SAE until resolution, stabilization or until the subject is no longer in the study as stated in the protocol.

When a reportable SAE is identified, the research assistant will initiate an SAE form, and the following individuals will be notified within 24 hours of the site's initial notification of the SAE:

- i. Study Co-Investigators.
- ii. The MUSC institutional review board (IRB). Committee meets monthly. Communication with the IRB is through email, memos, official IRB forms, and online reporting.
- iii. The NIH program officer.
- iv. The data safety monitoring board members.

If complete information is not available when the initial 24-hour SAE report is disseminated, follow-up information will be gathered to enable a complete assessment and outcome of the event. This information may include hospital discharge records, autopsy reports, clinic records, etc. The research staff will attach copies of source documents to the SAE report for review by the PI and for forwarding to the NIH program officer as appropriate. In addition, the PI will provide a signed, dated SAE summary report, which will be sent to the NICHD Medical Safety Officer within two weeks of the initial SAE report.

Study Safety. The potential risks and benefits and methods to minimize these risks are outlined above. Protocols for reported AEs and SAEs are outlined above. All unexpected AE and SAEs will be monitored until resolved. A detailed summary of all AEs will be prepared weekly by the research staff. At the weekly team meetings (or before if urgent), the research staff will report any premonitory symptoms of clinical deterioration.

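### The adverse-event follow-up rules set different end points, one of them an undefined exit from a one-visit study, and no systematic post-dose symptom query is described

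*Combined protocol and SAP*

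**What the plan says.** All of the following is in section 6 unless stated otherwise. The letters are used below.

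- **A. Non-serious AEs** (Documentation and Reporting): "If the AE is not serious, the information is recorded, managed medically as appropriate, and the event is followed until resolution".
- **B. SAEs** (same subsection): "SAEs are also recorded on the AE Form, managed medically as appropriate, and the event is followed until resolution".
- **C. Every AE and SAE** (same subsection, two paragraphs later): "the research staff will follow the AE/SAE until resolution, stabilization or until the subject is no longer in the study". The sentence ends by referring to the protocol for this last point.
- **D. Unexpected AEs and SAEs** (Study Safety): "All unexpected AE and SAEs will be monitored until resolved".
- **E. SAEs whose first 24-hour report is incomplete** (Documentation and Reporting): "follow-up information will be gathered to enable a complete assessment and outcome of the event". A signed summary report follows within two weeks.

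On the design, section 4.A states: "The present study will take place over one visit". The Laboratory Task Timeline puts the spray at 9:50am and the last assessment at 11:50am.

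On detection, Regulatory Issues states: "All research staff will identify any potential AEs during the course of the study from self-report data and administration of assessments and interviews". Documentation and Reporting adds that the PI makes sure AE information is captured at each visit, without naming questions or times. Potential Risks lists what the drug may do: "These risks include seizures, mental disturbances, nausea, vomiting, irregular heartbeat, high blood pressure, and unexpected bleeding or contraction of the uterus". That paragraph says these were noted in women given the drug intravenously, not intranasally.

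**The concern.** A follow-up rule should give one answer for a given event. Here the same event may have to be followed to resolution under one sentence and may be closed earlier under another. In a long trial the exit clause would seldom matter. In a one-visit trial it could apply on the day of dosing.

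Detection adds to the problem, because the sources named for finding AEs lie mostly before the spray, while most of the listed drug risks are physical events that would come after it. The plan relies on these counts: the DSMB is to monitor the rate and severity of AEs, and whether an AE is reportable depends partly on its being commoner than expected. Mild to moderate discomfort during the laboratory assessment is also defined as not an AE. Without a structured question, mild drug symptoms could be absorbed into that category. At stake are consistent follow-up of participants with unresolved events and the reliability of the AE rates in each arm.

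**Working it through.** The plan gives no figure to reproduce. The check compares the texts and does clock arithmetic on the timetable.

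**Step 1. Apply the rules to an event still unresolved when the visit ends.**

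| Event | Requires follow-up to resolution | Allows an earlier end |
|---|---|---|
| Non-serious, expected | A | C |
| Non-serious, unexpected | A, D | C |
| Serious | B, D (E expects later information) | C |

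Every row has at least one rule on each side. The conflict does not depend on the exit clause alone: an event that is stable but unresolved may be closed under C and may not under A, B or D.

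**Step 2. Look for a definition of exit.** Rule C defers to the protocol, but the available text does not say when a subject has left the study. End of visit, end of the SAE paperwork and withdrawal are all possible readings.

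**Step 3. Time from spray to end of visit, if exit means end of visit.**

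- Timetable: 11:50am − 9:50am = 120 minutes.
- Text of Data Collection Procedures (45 minutes to task 2, a 10-minute task, then 60 minutes): 45 + 10 + 60 = 115 minutes.
- Visit running a full 4 hours from 8:00am to noon: 12:00 − 9:50 = 130 minutes. With the spray 45 minutes before the 10:40am task, that is at 9:55am, it is 125 minutes.

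The range is 115 to 130 minutes, about 2 hours on every reading. The timetable spans 8:00am to 11:50am, or 230 minutes, which fits the stated 4-hour visit.

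**Step 4. Set the AE sources against the clock.**

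- Interview and questionnaire battery: done in the 8:00am block, before the spray.
- Self-report from 10:30am on: craving, distress, mood and feelings about the partner. Table 1 adds one item on constructive discussion. None is a physical symptom item.
- Physiology after dosing: skin temperature, skin conductance and heart rate. Blood pressure is not listed.
- After the visit: the PI contacts a participant the next day if that participant became distressed during or after an assessment. No contact is scheduled for everyone.

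**Step 5. Set the listed risks against those sources.** Staff on site could see a seizure or vomiting. Heart rate recording could show some rhythm change. The distress and mood items could reflect mental disturbance. Nausea, high blood pressure, and uterine bleeding or contraction have no scheduled post-dose question or measurement in the text and would depend mainly on a participant volunteering them.

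**The case against.** Most of the safety text already points one way. Rules A, B and D all require resolution, and for SAEs the plan also has 24-hour notification, later collection of hospital, clinic and autopsy records, a two-week summary and follow-up reports to the agencies. On this view rule C is stray wording. Detection also has support: CTRC medical staff are present to collect saliva, heart rate is recorded, an AE Form exists, weekly AE summaries are prepared, and participants hold the team's contact numbers. The listed risks come from intravenous use.

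Much of this stands, and it rules out several stronger readings that a reader might draw:

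- *That the plan plainly permits an SAE to be closed 2 hours after dosing.* This is only one reading of an undefined exit point, and the SAE text elsewhere assumes work after the visit.
- *That events after 11:50am are not captured.* The next-day contact for distress and the contact numbers give partial, passive capture. The supportable statement is that capture is not systematic.
- *That the protocol's description of the risk as minimal and manageable rests on these AE counts.* It rests on earlier studies, experience and literature.
- *That a zero-event upper limit on the AE rate measures the flaw.* Such a limit depends on the number treated and on complete ascertainment; it says nothing about how many events are missed.
- *That the AE Form has no symptom items.* The form is not reproduced, so only the absence of a described query can be asserted.

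The objection does not remove the conflict. Rule C covers every AE and SAE and is as binding as the others, and the expectation of post-visit SAE work makes it harder to reconcile. Nor does any of the support amount to a described, systematic post-dose query.

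**Conclusion.** The concern holds in this form. Rules A, B and D conflict with rule C for every class of AE. The exit point in C is undefined and, if read as the end of the visit, falls about 2 hours after the spray (115 to 130 minutes). That timing is an inference from the timetable and assumes this reading of exit. Separately, no systematic post-dose symptom query, blood pressure measurement or routine post-visit contact is described, so the listed risks are captured only partially or passively.

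This should be fixed because it affects participant follow-up and the AE rates that the DSMB reviews. It does not alter any efficacy estimate, sample size, power or alpha. How many events would be missed cannot be estimated from the documents.

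**What to change.** 1. Reconcile the sentences in Documentation and Reporting and in Study Safety to a single follow-up end point for each class of event. Which end point applies is for the sponsor and investigators to decide.
2. Define when a subject has left the study and when AE collection ends.
3. Add a short structured AE query to the AE Form, covering the events listed under Potential Risks. Ask it of each participant before dosing and again at the existing 11:50am assessment, once the subjective ratings at that time point are complete. Asked then, the post-dose query cannot influence those ratings. At the 10:30am subjective baseline it could shift distress scores or prompt guesses about treatment in a double-blind study.
4. The sponsor may also consider extending the existing next-day contact to all participants.

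The cost is some protocol wording, a brief addition to a form and a few minutes of staff time per participant. If item 4 is adopted, add about 72 short calls over the 2-year enrolment period for 36 couples (36 × 2 = 72). Slightly more minor AEs will be recorded. Clinical handling of any event stays with the investigators.
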